A Phase II Trial of Protease Inhibitor, Nelfinavir (NFV), Given with Definitive, Concurrent Chemoradiotherapy (CTRT) in Patients with Locally-Advanced, Human Papilloma Virus (HPV) negative, Squamous Cell Carcinoma of the Head and Neck

Regulatory Sponsor: [name]
University of Pennsylvania, Department of Radiation Oncology
[name]
[name]
[contact]
[contact]

Sub-Investigators: Radiation Oncology – [name], PhD
Radiation Oncology – [name]
Radiation Oncology- [name]
Radiology – [name]
Radiology – [name], PhD
[name]

Collaborators: Radiation Oncology- [name]
Radiation Oncology- [name]
Medical Oncology – [name]
Medical Oncology – [name], MPH
Medical Oncology- [name]
Otolaryngology – [name], MD
Otolaryngology – [name]
Otolaryngology – [name]
Otolaryngology – [name]
Biostatistician- [name], MS

Study Product: Nelfinavir
¹⁸F-FMISO

Protocol Number: 817878

CONFIDENTIAL

This document is confidential and the property of the University of Pennsylvania. No part of it may be transmitted, reproduced, published, or used by other persons without prior written authorization from the study sponsor.

Table of Contents

STUDY SUMMARY	3
1 INTRODUCTION.....	4
2 STUDY OBJECTIVES.....	6
3 STUDY DESIGN.....	7
4 SUBJECT SELECTION AND WITHDRAWAL.....	8
5 STUDY DRUG	14
6 STUDY PROCEDURES.....	19
7 STATISTICAL PLAN.....	255
8 SAFETY AND ADVERSE EVENTS	27
9 DATA HANDLING AND RECORD KEEPING	33
10 DATA AND SAFETY MONITORING PLAN.....	35
11 ETHICAL CONSIDERATIONS.....	36
12 STUDY FINANCES.....	36
13 PUBLICATION PLAN.....	36
14 REFERENCES.....	37

List of Abbreviations

Chemoradiotherapy:	CTRT
Computed Tomography:	CT
Head and neck squamous cell carcinoma	HNSCC
Nelfinavir:	NFV
Human Papilloma Virus:	HPV
Positron Emission Tomography	PET
Tumor to Muscle Ratio	TM

Study Summary

Title	A Phase II Trial of Protease Inhibitor, Nelfinavir (NFV), Given with Definitive, Concurrent Chemoradiotherapy (CTRT) in Patients with Locally-Advanced, Human Papilloma Virus (HPV) negative, Squamous Cell Carcinoma of the Head and Neck
Short Title	Definitive Nelfinavir with Chemoradiation for Head and Neck Cancer
Protocol Number	817878
Phase	Phase II
Methodology	Open Label
Study Duration	5 years
Study Center(s)	University of Pennsylvania; Philadelphia VA Medical Center
Objectives	To determine locoregional control in patients with locally advanced, HPV-negative head and neck cancer treated with definitive NFV + CTRT.
Number of Subjects	28
Diagnosis and Main Inclusion Criteria	Stage III, IVa, or IVb squamous cell carcinoma of the oral cavity, oropharynx, larynx, or hypopharynx with ECOG performance status 0-2
Study Product, Dose, Route, Regimen	
Nelfinavir (Viracept®) 1250 mg By mouth two times a day Medicine should be taken with food, preferably high in fat.
 
¹⁸F-FMISO 5-10 mCi Intravenous bolus injection

Duration of administration	Treatment to start 7-14 days prior to radiation and continued throughout radiation and standard chemotherapy.
Reference therapy	Combination of standard chemotherapy and radiation therapy
Statistical Methodology	This is a single arm, phase II study of nelfinavir (1250 mg given po bid) and concurrent chemoradiotherapy in locally advanced head and neck cancer. Locoregional control will be compared to published historical results. There will be a total of 28 patients enrolled on the study.

1 Introduction

This is a Phase II trial of definitive chemoradiotherapy (CTRT) given with the protease inhibitor, Nelfinavir (NFV), in patients with locally advanced head and neck cancer. Eligible patients will receive a “lead-in” period of Nelfinavir (1250 mg po bid) for 7-14 days prior to initiation of CTRT. Nelfinavir will then be given concurrently with platinum-based chemotherapy and radiation therapy (planned total dose of 70 Gy over 7 weeks).

All patients will also undergo the following:

- 1) ^{18}F -FMISO PET/CT: this scan assesses tumor hypoxia. Patients will undergo 2 separate ^{18}F -FMISO PET/CT scans: the first at baseline to determine baseline tumor hypoxia, the second after a 7-14 day lead-in of NFV prior to CTRT (to determine change in tumor oxygenation secondary to NFV). Six patients will receive 3 separate ^{18}F -FMISO PET/CT, the first at baseline to determine baseline tumor hypoxia, the second also at baseline to determine reliability of the scan for test-retest purposes, the third after a 7-14-day lead-in of NFV.
- 2) ^{18}F -FDG PET/CT: this scan assesses glucose uptake. Patient will undergo 2 separate ^{18}F -FDG PET/CT scans: the first at baseline as part of routine clinical care, for purposes of radiation treatment planning and the second after a 7-14 day lead-in of NFV prior to CTRT (to determine change in tumor glucose uptake secondary to NFV).

The primary objective of the study will be to determine whether NFV, given with definitive CTRT, will improve locoregional control in locally advanced head and neck cancer.

Secondary objectives of this study include:

- To determine the effect of NFV on hypoxia, as assessed by ^{18}F -FMISO PET/CT.
- To determine the effect of NFV on glucose metabolism, as assessed by ^{18}F -FDG PET/CT, and possible associations between hypoxia and glucose metabolism.

1.1 Background

Radiation therapy is a commonly used treatment for cancer. Despite the use of sophisticated, state-of-the-art techniques, local-regional control is often not achieved in many cases, leading to recurrence. A case in point is locally advanced head and neck squamous cell carcinoma (HNSCC) cancer, which has a 5-year locoregional control rate of 33.7% following combined chemoradiation (1). In 2012 there were over 50,000 new cases of HNSCC with approximately 11,500 deaths (2). While the overall prognosis of HNSCC appears to be improving, this may be due to changing demographics with a higher percentage of cases associated with HPV, which appears to have a better prognosis than HPV-negative HNSCC (3).

Previous studies of hypoxic radiosensitizers have shown promise. In the TROG 02.02 phase III trial of definitive head and neck chemoradiation +/- tirapazamine, there was a trend favoring the tirapazamine arm for improved locoregional control in patients who were HPV-negative (5). For patients identified to have hypoxic disease via F-MISO PET scanning who did not receive tirapazamine, locoregional control was 38% at a median followup of 3.6 yrs, versus 95% in similar patients who received tirapazamine (6).

One approach for increasing the therapeutic window of radiotherapy is to combine radiation therapy with biological agents. Over the past few years, we have focused on agents that can modulate the tumor microenvironment to improve radiation response (7, 8). One particular

agent, nelfinavir, has been widely used in HIV patients with well-characterized pharmacokinetics and low toxicity profile. NFV inhibits the PI3K/Akt/mTOR pathway, which we believe increases the intrinsic radiosensitivity of cells (9-11). However, the effects of NFV on the *in vivo* radiation response appear to be greater than those seen *in vitro*, which led us to investigate whether the drug might have effects on the tumor microenvironment (TME) that could improve the radiation response. Indeed, we and others have found that NFV treatment of mice bearing tumor xenografts leads to improved oxygenation (10, 12). This is potentially clinically important because hypoxia is a factor associated with poor prognosis in many cancers, including HNSCC (13-15). Hypoxic cells require higher doses of radiation compared to oxic cells to achieve the same level of killing due to the requirement of oxygen to elicit maximal DNA damage through the oxidation of DNA and other target radicals (16). This leads us to one of our hypotheses that a major mechanism by which NFV improves the radiation response *in vivo* is by decreasing tumor hypoxia.

Determinants & Mechanisms of Nelfinavir Response

A phase I/II trial at Penn has been conducted in which NFV was combined with cisplatin-based (as with this protocol) chemotherapy and radiation for stage IIIA/B non-small cell lung cancer (17). The phase I trial showed that NFV given at a dose of 1250 mg (which was found to be the MTD) orally twice a day was well tolerated by these patients treated with chemoradiation. There were no dose limiting toxicities on this 16 patient trial, and no patients required dose attenuation of chemotherapy or nelfinavir. This trial did not test the idea than NFV can modulate tumor hypoxia or include hypoxia imaging. There are several methods that are available to measure hypoxia in human tumors including Eppendorf needle electrode and 2-nitroimidazole binding (18). 2-nitroimidazole drugs are reduced and form adducts with protein thiols in hypoxic cells (19).

1-H-1-(3-[18F] fluoro-2-hydroxypropyl)-2-nitroimidazole also known as

[¹⁸F]fluoromisonidazole or ¹⁸F-FMISO is a positron emitting radiopharmaceutical that has been studied *in vivo* in humans for measurement of regional hypoxia in a number of tumor types with positron emission tomography (PET/CT). Grierson et al described synthesis methods that yielded high specific activity ¹⁸F-FMISO for use in PET imaging studies [Grierson 1989]. Fluoromisonidazole is a congener of misonidazole, which is an electron affinic drug with selective binding in cells with reduced pO₂ [Chapman 1981, 1983, Franko 1984]. An ideal hypoxia-imaging agent should distribute independently of blood flow, which is best achieved when the partition coefficient of the tracer is close to unity. Under these circumstances, imaging data can be acquired at a time when the intracellular tracer distribution has equilibrated with the tracer in plasma near the cells. ¹⁸F-FMISO is an azomycin-based hypoxic cell sensitizer, because [¹⁸F]FMISO partitions nearly equally between octanol and water, normoxic tissues have T/B (tissue/blood) pixel values of almost 1.0. The hypoxic part of a tumor can be characterized by the maximum T/B value or by the total number of pixels with T/B greater than some threshold. These pixels are summed and multiplied by the known mL/pixel to calculate hypoxic volume, (HV). Rasey et al characterized the binding characteristics of ¹⁸F-FMISO in cells *in vitro* at various oxygen levels and in animal studies of tumors. Results demonstrated the oxygen dependent binding of radiolabeled fluoromisonidazole *in vitro* and *in vivo* and supported the use of ¹⁸F-FMISO as a quantitative hypoxia probe using the measurement of retention of ¹⁸F-FMISO in tumor vs blood and normal tissue to calculate hypoxic fraction in tumors [Rasey 1989]. ¹⁸F-FMISO PET/CT provides a valuable non-invasive method to measure viable hypoxic cells in human malignancies, which may aid in better understanding mechanisms of resistance and response to treatments, such as radiation or anti-angiogenesis therapies.

The injectable dose of ^{18}F -FMISO for this study will be $\leq 10\text{mCi}$ (with an expected range of 5- 10 mCi at the time of injection) which has been shown to generate high quality PET/CT images with acceptable radiation dose to subjects, the drug mass injected for each study will be $\leq 15\text{ }\mu\text{g}$.

In the current protocol we focus on the central hypothesis that NFV will result in a decrease in tumor hypoxia in head and neck tumors, and that this alteration in hypoxia plays a role in its ability to radiosensitize, leading to improved treatment outcomes. We also hypothesize that: 1) the effect of NFV on hypoxia can be assessed by ^{18}F -EF5 or by ^{18}F -FMISO,(the initial 15 subjects have been completed using ^{18}F -EF-5) and 2) changes in hypoxia will correlate with changes in glucose metabolism (decrease in glucose uptake), as assessed by ^{18}F -FDG PET/CT scanning.

Summary

We propose a clinical trial of the HIV protease inhibitor, nelfinavir, and concurrent, definitive chemoradiation in patients with locally advanced, HPV-negative head and neck cancer. This is an ideal population because of their poor prognosis with current therapy and the fact that HNSCC tumors are known to be hypoxic. Furthermore, activation of the EGFR/PI3K pathway is common in HNSCC, identified in 74% of cases in one report (30), so these tumors should respond to NFV. Assessment of tumor oxygenation response to NFV will be made using ^{18}F -FMISO PET/CT scanning and correlation of hypoxia with glucose metabolism will be assessed via ^{18}F -FDG PET/CT scanning. If the combination of NFV and radiation is found to be effective in this group of patients, it could then be extended to patients with other cancers.

2 Study Objectives

2.1 Primary Objective

To determine locoregional control for patients with locally advanced, HPV-negative head and neck cancer, treated with definitive NFV + CTRT and compare it to published historical results.

2.2 Secondary Objectives

- 2.2.1** To determine the effect of NFV on hypoxia as assessed by ^{18}F -FMISO PET/CT scanning.
- 2.2.2** To determine whether glucose metabolism (as assessed by ^{18}F -FDG PET/CT) is affected by NFV, and whether this corresponds to a decrease in ^{18}F -FMISO uptake.

3 Study Design

3.1 General Design

Twenty-eight subjects will be enrolled on this clinical trial investigating the efficacy of definitive NFV + CTRT for locally advanced head and neck cancer. Patients will also receive two ¹⁸F-FMISO PET/CT studies: the first at baseline to determine baseline tumor hypoxia, the second after a 7-14 day lead-in of NFV prior to CTRT (to determine change in tumor oxygenation secondary to NFV). Additionally, patients will undergo 2 separate ¹⁸F-FDG PET/CT scans: the first at baseline as part of routine clinical care, for purposes of radiation treatment planning and the second after a 7-14 day lead-in of NFV prior to CTRT (to determine change in tumor glucose uptake secondary to NFV). The research ¹⁸F-FMISO PET/CT and ¹⁸F-FDG PET/CT studies are **mandatory**, in order to participate on this clinical trial. Only under circumstances where the PI, [name], deems the patient is unable to comply with the PET/CT requirements will its completion be excused and allow the patient to remain on the study.

3.2 Primary Study Endpoints

The intent of this protocol is to determine the efficacy of NFV + CTRT for locally advanced, HPV-negative head and neck cancer. Therefore, the primary endpoint will be locoregional control. However, secondary objectives will be (1) to determine the effect of NFV on hypoxia as assessed by ¹⁸F-FMISO PET/CT imaging (the initial 15 subjects were imaged with ¹⁸F-EF5) and (2) determine whether glucose metabolism (as assessed by ¹⁸F-FDG PET/CT) is affected by NFV, and whether this corresponds to a decrease in ¹⁸F-FMISO uptake. NFV responders have a better treatment outcome than NFV non-responders will be tested by comparing PFS between these groups. The definition of "NFV responder" requires greater knowledge about the distribution and variance of the baseline T:M ratio. For example, a decrease in T:M ratio to <1.25 or percent decrease from baseline of >50% may be reasonable definitions.

3.3 Secondary Study Endpoints

¹⁸F-FMISO PET/CT

Patients will receive two hypoxia PET/CT scans with either ¹⁸F-FMISO or ¹⁸F-EF5 (initial 15 subjects were completed using EF-5, subsequent subjects will be imaged with FMISO): the first at baseline to determine baseline tumor hypoxia, and the second after a 7-14 day lead-in of NFV prior to CTRT (to determine change in tumor oxygenation secondary to NFV). Tumor regions of interest (ROIs), corresponding to the primary tumor site and pathologic lymph nodes will be drawn with the help of CT images. Tumor to muscle ratios (TMR) will be determined for each ROI. A TMR of ≥ 1.3 will be considered significant for hypoxia, and a reasonable starting point in which the outcome of the addition of NFV to CTRT can be evaluated. The ability of NFV to reduce tumor hypoxia will be tested by comparing pre and post-NFV hypoxia (i.e., ¹⁸F-FMISO uptake expressed as a TMR) by Student's paired t-test.

¹⁸F-FDG PET/CT

Patients will undergo 2 separate ¹⁸F-FDG PET/CT scans: the first at baseline as part of routine clinical care, for purposes of radiation treatment planning and the second after a 7-14 day lead-in of NFV prior to CTRT (to determine change in tumor glucose uptake secondary to NFV). That

change in hypoxia will correlate with change in glucose uptake will be tested by Pearson's correlation.

That baseline hypoxia and glucose metabolism are predictive of treatment outcome will be tested by Cox regression analysis.

NCI Common toxicity grades will be employed.

4 Subject Selection and Withdrawal

4.1 Inclusion Criteria

- 4.1.1** Patients \geq 18 years old.
- 4.1.2** Histologically confirmed diagnosis of squamous cell carcinoma of the oral cavity, oropharynx, larynx, or hypopharynx AJCC 7th edition stages III, IVa, or IVb, p16-negative on immunohistochemistry (p16 testing to be performed only on oropharynx cancers, as it has not been found to be prognostic or standard of care outside of cancers of the oropharynx).
- 4.1.3** Determined by the treating physician to be a candidate for organ preserving, concurrent standard chemotherapy and radiation therapy to the head and neck with definitive intent.
- 4.1.4** ECOG Performance Status 0-2
- 4.1.5** Patients must sign an informed consent document that indicates they are aware of the investigational nature of the treatment in this protocol as well as the potential risks and benefits.
- 4.1.6** Ability to understand and the willingness to sign a written informed consent.

4.2 Exclusion Criteria (All laboratory studies must be completed 1 month prior to signing consent)

- 4.2.1** Prior radiation therapy (defined as more than 5 fractions of head and neck radiotherapy, less than 10 Gy total prior radiation) to the head and neck
- 4.2.2** Prior chemotherapy within the past 5 years
- 4.2.3** Previous therapy with a human immunodeficiency virus (HIV) protease inhibitor
- 4.2.4** Females who are pregnant at the time of screening will not be eligible for this study, urine pregnancy test will be performed at screening and prior to injection of FMISO in women of child-bearing potential.
- 4.2.5** Patients with known HIV disease. These patients have a high probability of treatment with anti-retroviral therapy which may interact with the nelfinavir.
- 4.2.6** Absolute Neutrophil Count \leq 1500 per mm³
- 4.2.7** Platelet count \leq 100,000 per mm³
- 4.2.8** Serum creatinine $>$ 1.5 times the upper limit of normal
- 4.2.9** Serum AST or ALT $>$ 2 times the upper limit of normal
- 4.2.10** Serum bilirubin $>$ 1.2 mg/dl
- 4.2.11** Weight loss of $>$ 10% over the past 6 months which is due to tumor wasting syndrome
- 4.2.12** Distant metastases
- 4.2.13** Patients receiving the following drugs that are contraindicated with NFV will be excluded.

Antiarrhythmics: amiodarone, quinidine	CONTRAINDICATED due to potential for serious and/or life threatening reactions such as cardiac arrhythmias
Antimycobacterial: rifampin	May lead to loss of virologic response and possible resistance to VIRACEPT or other coadministered antiretroviral agents.
Ergot Derivatives: dihydroergotamine, ergonovine, ergotamine, methylergonovine	CONTRAINDICATED due to potential for serious and/or life threatening reactions such as acute ergot toxicity characterized by peripheral vasospasm and ischemia of the extremities and other tissues.

Herbal Products: St. John's wort (hypericum perforatum)	May lead to loss of virologic response and possible resistance to VIRACEPT or other coadministered antiretroviral agents.
HMG-CoA Reductase Inhibitors: lovastatin, simvastatin	Potential for serious reactions such as risk of myopathy including rhabdomyolysis.
Neuroleptic: pimozide	CONTRAINDICATED due to potential for serious and/or life threatening reactions such as cardiac arrhythmias.
Proton Pump Inhibitors	Omeprazole decreases the plasma concentrations of nelfinavir. Concomitant use of proton pump inhibitors and VIRACEPT may lead to a loss of virologic response and development of resistance. Patients that have been off of proton pump inhibitors for 14 days before enrollment will be allowed to participate.
Sedative/Hypnotics: midazolam, triazolam	CONTRAINDICATED due to potential for serious and/or life threatening reactions such as prolonged or increased sedation or respiratory depression.

4.2.15 Patients receiving the following drugs will be clinically evaluated by the PI as to whether dosage/medication can and should be changed to permit patient on study:

Anti-Convulsants: carbamazepine, Phenobarbital	↓ nelfinavir	May decrease nelfinavir plasma concentrations. VIRACEPT may not be effective due to decreased nelfinavir plasma concentrations in patients taking these agents concomitantly.
Anti-Convulsant: phenytoin	↓ phenytoin	Phenytoin plasma/serum concentrations should be monitored; phenytoin dose may require adjustment to compensate for altered phenytoin concentration.
Anti-Mycobacterial: rifabutin	↑ rifabutin ↓ nelfinavir (750 mg TID) ↔ nelfinavir (1250 mg BID)	CONTRAINDICATED due to potential for serious and/or life threatening reactions such as acute ergot toxicity characterized by peripheral vasospasm and ischemia of the extremities and other tissues.
PDE5 Inhibitors: sildenafil, vardenafil, tadalafil	↑ PDE5 inhibitors	Concomitant use of PDE5 inhibitors and VIRACEPT should be undertaken with caution. If concomitant use of PDE5 inhibitors and VIRACEPT is required, sildenafil at a single dose not exceeding 25 mg in 48 hours, vardenafil at a single dose not exceeding 2.5 mg in 72 hours, or tadalafil at a single dose not exceeding 10 mg dose in 72 hours, is recommended.

HMG-CoA Reductase Inhibitors: atorvastatin, rosuvastatin	↑ atorvastatin ↑ rosuvastatin	Use lowest possible dose of atorvastatin or rosuvastatin with careful monitoring, or consider other HMG-CoA reductase inhibitors such as pravastatin or fluvastatin in combination with VIRACEPT.
Immuno- suppressants: cyclosporine, tacrolimus, sirolimus	↑ immuno- suppressants	Plasma concentrations may be increased by VIRACEPT.
Narcotic Analgesic: methadone	↓ methadone	Dosage of methadone may need to be increased when coadministered with VIRACEPT.
Oral Contraceptive: ethinyl estradiol	↓ ethinyl estradiol	Alternative or additional contraceptive measures should be used when oral contraceptives and VIRACEPT are coadministered.
Macrolide Antibiotic: azithromycin	↑ azithromycin	Dose adjustment of azithromycin is not recommended, but close monitoring for known side effects such as liver enzyme abnormalities and hearing impairment is warranted.
Inhaled/nasal steroid: fluticasone	↑ fluticasone	Concomitant use of fluticasone propionate and VIRACEPT may increase plasma concentrations of fluticasone propionate. Use with caution. Consider alternatives to fluticasone propionate, particularly for long-term use.
Antidepressant: trazodone	↑ trazodone	Concomitant use of trazodone and VIRACEPT may increase plasma concentrations of trazodone. Adverse events of nausea, dizziness, hypotension and syncope have been observed following coadministration of trazodone and nelfinavir. If trazodone is used with a CYP3A4 inhibitor such as VIRACEPT, the combination should be used with caution and a lower dose of trazodone should be considered.

4.2.16 Women of childbearing potential who have a positive result on screening urine pregnancy test.

4.2.17 Subjects with moderate-severe renal disease.

4.2.18 History of allergic reactions attributed to Flagyl (metronidazole), which has a chemical structure similar to FMISO.

4.2.19 Uncontrolled intercurrent illness including, but not limited to symptomatic congestive heart failure, unstable angina pectoris, or psychiatric

illness/social situations that would limit compliance with study requirements.

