5.3 Method for Assigning Subjects to Treatment Groups

The subjects will be identified for this study based on their inclusion/exclusion criteria. Since this is a phase II study, there is no assignment to treatment groups and all subjects are treated as per protocol.

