5.6 Prior and Concomitant Therapy

Any prior therapy is permitted with the exception of radiation therapy to the head and neck (defined as more than 5 fractions and more than 10 Gy) and any standard chemotherapy within the last 5 years.

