6.4 Radiation Therapy

Radiation therapy in all subjects will begin 7 to 14 days after the initiation of nelfinavir.

Simulation for treatment is required. PET/CT-based treatment planning is required. Treatment will be delivered via intensity-modulated photon or pencil-beam proton radiotherapy. All fields will be treated every session. Interruptions in therapy should be discussed with the principal investigator but will be instituted at the discretion of the attending radiation oncologist.

The gross tumor volume, clinical treatment volume, and planning treatment volume are defined according to ICRU 50. Dose calculation should be performed using inhomogeneity corrections to account for differences in tissue density across the head and neck region. The total dose to gross disease will be 70 Gy. This will be administered in 2.0 Gy daily fractions. Regional lymph node regions may be treated, as dictated by the clinical situation. High-risk elective nodal regions would receive anywhere from 59.5 to 63 Gy, administered in 1.7-1.8 Gy daily fractions, while low-risk elective nodal regions would receive anywhere from 56 to 59.5 Gy, administered in 1.6- 1.7 Gy daily fractions. Treatment will be continuous, 5 days per week for 7 consecutive weeks.

Normal tissue doses: Dose-volume histograms should be performed for organs at risk, such as the spinal cord, brainstem, optic nerves and chiasm, pharyngeal constrictors, and mandible. The

maximal spinal cord dose should not exceed 45 Gy. The maximal dose to the brainstem, optic nerves and chiasm, should not exceed 54 Gy. The mean dose to the pharyngeal constrictors should not exceed 50 Gy. The maximal dose to the mandible (not included in the planning treatment volume) should not exceed 70 Gy.

6.5 ¹⁸F-FMISO PET/CT Imaging

Two ¹⁸F-FMISO PET/CT imaging scans to assess tumor oxygen level in response to treatment with Nelfinavir will be performed. Pregnancy tests will be performed prior to each scan. The first ¹⁸F-FMISO PET/CT will occur shortly after enrollment, prior to administration of any therapy. The second will occur after a 7-14 day period of NFV alone.

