9.3 Flow of Subject Data

Study entry: Each patient will be evaluated for this study based upon the inclusion and exclusion criteria. If a patient is found to be eligible for the study, an eligibility checklist will be completed after the patient has signed an informed consent form. The patient will be assigned a study number. A list of the subjects with the assigned study numbers will be kept on a confidential computer file in the Department of Radiation Oncology, University of Pennsylvania.

Treatment: After study enrollment, the subject will undergo treatment planning for chemoradiotherapy as per standard clinical care. The subject will begin oral nelfinavir 7-14 days prior to the initiation of radiotherapy. The principal or a co-investigator will fill out a radiotherapy prescription form as per routine clinical care. The investigator will also complete a

prescription form for nelfinavir. The study coordinator will double-check the nelfinavir prescription.

Imaging: Copies of all imaging for these studies will be maintained by the Department of Radiology, Division of Nuclear Medicine, at the University of Pennsylvania.

Follow-up: The clinical status and laboratory results of the subjects will be recorded on a flow sheet and on the CRF. Toxicity forms will be maintained for each subject and will be evaluated up to the first standard of care follow-up visit after completion of radiation. The principal investigator will verify the grades and attribution of the toxicities for each subject. Subjects will be followed for survival for the remainder of the follow-up.

10 Data and Safety Monitoring Plan

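### Exclusion 4.2.1 and section 5.6 put opposite dose limits on the prior head-and-neck radiotherapy that bars entry; the inequality in 4.2.1 is most likely reversed

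*Combined protocol and SAP*

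**What the plan says.** The rule on prior head-and-neck radiotherapy appears twice in the protocol.

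- **Section 4.2, criterion 4.2.1** lists prior head-and-neck radiotherapy as an exclusion, "defined as more than 5 fractions of head and neck radiotherapy, less than 10 Gy total prior radiation".
- **Section 5.6** states it as an exception to what is allowed: "Any prior therapy is permitted with the exception of radiation therapy to the head and neck". The full exception reads "radiation therapy to the head and neck (defined as more than 5 fractions and more than 10 Gy".

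Other sections bear on how the rule is used.

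- Section 5.3 says that subjects will be "identified for this study based on their inclusion/exclusion criteria". Section 9.3 says "Each patient will be evaluated for this study based upon the inclusion and exclusion criteria", with an eligibility checklist completed after consent.
- Criterion 4.1.3, which concerns treatment of definitive intent, requires that the patient be "Determined by the treating physician to be a candidate for organ preserving, concurrent standard chemotherapy and radiation therapy to the head and neck".
- Section 6.4 prescribes 70 Gy to gross disease in 2.0 Gy fractions and says that the "maximal spinal cord dose should not exceed 45 Gy". It does not say whether dose from an earlier course counts.

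**The concern.** The two definitions share the treatment, the body site, the fraction limit and the 10 Gy figure. Only the direction of the dose inequality differs, and nothing else in the document reconciles them.

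An exclusion for prior irradiation would be expected to keep out heavily treated patients and perhaps tolerate a trivial dose. Taken literally, with its two limits joined by *and*, 4.2.1 does the reverse.

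This matters because 4.2.1 is in the list that sections 5.3 and 9.3 make the basis for screening, and 5.6 is not. The list controls entry to a 70 Gy course. Screeners could reach different decisions on the same patient depending on which section they consult and how they read the comma. A later auditor could not settle from the text who was right.

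**Working it through.** There is no design figure to reproduce, so the check applies each definition to the same courses.

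**Inputs.** Let F be the number of prior head-and-neck fractions and D the total prior dose in Gy. The limits come from 4.2.1 and 5.6. The 2.0 Gy fraction size comes from 6.4. The example courses are illustrations, not patients in the document.

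**Rules.** A patient is excluded if:

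- 4.2.1, comma read as *and*: F > 5 and D < 10
- 4.2.1, comma read as *or*: F > 5 or D < 10
- 5.6: F > 5 and D > 10

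| Prior course | 4.2.1 (*and*) | 4.2.1 (*or*) | 5.6 |
|---|---|---|---|
| 6 fractions, 9 Gy | excluded | excluded | allowed |
| 35 fractions, 70 Gy | not excluded | excluded | excluded |
| 1 fraction, 8 Gy | not excluded | excluded | allowed |
| 5 fractions, 40 Gy | not excluded | not excluded | allowed |

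The 35 fractions are 70 / 2.0. Under *and*, 4.2.1 conflicts with 5.6 on the first and second courses, and the two excluded sets do not overlap at all. Under *or*, it conflicts on the first and third. The first is in conflict under both readings.

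**A third reading.** Suppose the dose in 4.2.1 was meant as the amount tolerated. Then 4.2.1 excludes F > 5 with D of 10 or more, which matches 5.6 except at exactly 10 Gy. But the dose stands inside the definition of what is barred, so the reader has to supply that meaning.

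**Which section is wrong?** More than 5 fractions means at least 6.

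- For 6 fractions to total under 10 Gy, the mean must be below 10 / 6 = 1.67 Gy per fraction.
- At the protocol's 2.0 Gy, 6 fractions give 6 × 2.0 = 12 Gy. Under *and*, 4.2.1 would then exclude nobody treated at that fraction size.
- At 2.0 Gy, 5 fractions give 5 × 2.0 = 10 Gy. More than 5 fractions and more than 10 Gy are therefore matching limits, as 5.6 has them.

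This points to 4.2.1 as the section with the slip. It is an inference; the document does not say so.

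**After the correction.** With the dose limit in 4.2.1 changed to more than 10 Gy and joined by *and*, both sections exclude F > 5 with D > 10, and the conflicts disappear.

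**The case against.** The strongest reply is that little can go wrong in practice. If both sections are enforced as bars with the *and* reading, together they exclude every course of more than 5 fractions except one of exactly 10 Gy. A patient with 70 Gy in 35 fractions is kept out by 5.6 whatever 4.2.1 says, so the error can only exclude too many. Criterion 4.1.3 adds a physician's judgement, and sections 9.1 and 9.2 require an investigator to sign a confirmation of eligibility. The course in conflict under both readings is unusual (9 / 6 = 1.5 Gy per fraction), and a radiation oncologist would probably see the slip. The *or* reading is strained, given that 5.6 uses *and*. The eligibility checklist is not in the document and may already be right.

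Much of this stands. The safety risk is reduced, the table shows how the rules conflict and not how often, and the 40 Gy course is not part of the inconsistency because both sections treat it alike.

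It does not remove the point. The protection from 5.6 depends on the screener consulting a section outside the exclusion list. Criterion 4.1.3 sets no limit on prior dose. Neither decides whether 9 Gy in 6 fractions is eligible. That the slip is easy to spot makes it cheap to correct, but gives no reason to leave it.

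**Conclusion.** The concern holds. Sections 4.2.1 and 5.6 contradict each other on an operative eligibility limit, and the inequality in 4.2.1 is most likely reversed. That attribution rests on the fractionation arithmetic and on the purpose of such an exclusion.

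This is a drafting error that should be corrected. The document gives no sign that an ineligible patient was enrolled, and the number affected may be zero. Power, sample size and type I error are unchanged, and no effect on the locoregional control estimate can be quantified. What remains is a rule that can be applied in different ways at entry to a 70 Gy course.

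**What to change.** 1. In 4.2.1, change the dose limit from less than 10 Gy to more than 10 Gy, to match 5.6.
2. Have the clinical team confirm whether the fraction and dose limits are joined by *and* or *or*, and how exactly 10 Gy is handled. With *and*, a few large fractions such as 5 × 8 Gy = 40 Gy would still be allowed. With *or*, that course would be excluded, but so would 9 Gy in 6 fractions.
3. Use identical wording in 4.2.1, 5.6 and the eligibility checklist described in 9.3.
4. Check prior radiotherapy against the corrected rule for the patients already enrolled. There are at least 15, since section 3.2 says "the initial 15 subjects were imaged with" the earlier tracer, EF5.

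The cost is a one-line amendment to 4.2.1, matching edits to 5.6 and the checklist, and a short record review. The sample size and the analysis stay as they are.
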